#### 15.9.4 Critical COVID-19 disease

A critical COVID-19 disease case is defined as a COVID-19 disease case being admitted to the ICU. The clinical and laboratory characteristics of the critical COVID-19 disease cases will be described (Annex 1).

# 15.10 Covariates

The complete dataset can be found in Annex 4, and is summarised in Table 3. Some covariates are mandatory to collect for all participating study sites. All covariates are both being collected for prospective and retrospective subjects, if available.

Age at hospital admission Calculated based on date of birth and date of	
admission	
Male, female	х
Binary	х
Binary	х
	admission Male, female Binary

#### Table 3. Study covariates

Cardiovascular	Binary	х
disease		
Hypertension	Binary	х
Chronic kidney	Binary	х
disease		
Type 2 diabetes	Binary	х
Cancer	Binary	х
Immunodeficiency (or	Binary	х
organ transplant)		
Chronic liver disease	Binary	х
Pregnancy	Binary	х
Trimester	First, second, third	х
Body mass index (BMI)	Continuous	х
Smoking history	Never smoker, former smoker (smokefree for at least	
	28 days), current smoker	
Vaccination history	Being vaccinated with at least one influenza vaccine	Х
influenza	within 12 months prior to SARI hospital admission	
Vaccination history	Year of vaccination	х
pneumococcus		
Long-term care facility	Binary	
residence		
Healthcare worker	Binary	
Healthcare worker with	Binary	
direct contact to COVID-		
19 patients		
Precautionary health	Participants will be asked about their precautionary	
behavior	health behavior (e.g. wearing face masks, using hand	
(see Annex 3 for survey)	sanitiser, going to public places)	
Previous SARS-CoV-2	Participants will be asked about prior COVID-19 tests	х
infection	and test results	
Anti-SARS-CoV-2 antibody	Binary, brand, start date of treatment	
products or other drugs		
indicated for pre-		
exposure prophylaxis for		
SARS-CoV-2 infection		
within 6 months prior to		
hospitalisation		
Anti-SARS-CoV-2 antibody	Binary, brand, start date of treatment	
products or other drugs		
indicated for post-		
exposure prophylaxis for		
SARS-CoV-2 infection		

within 6 months prior to	
hospitalisation	
Anti-SARS-CoV-2 antibody	Binary, brand, start date of treatment
products or antiviral	
drugs indicated for	
treatment post-symptom	
onset leading to the	
current hospitalisation	

#### **15.11** Sample size considerations

#### 15.11.1 Targeted sample size

The sample size requirements and assumptions will be different for the different vaccine brands. In case the parameter settings used for these sample size calculations are very different from what is observed in the study, the sample size calculations will be updated accordingly for both interim and final analysis.

#### 15.11.1.1 Primary vaccination

For the analysis of interest, the number of required COVID-19 cases to obtain precise estimates were obtained using a simulation-based sample size calculation. The simulation study reflects the design of the current study; a multi-site TNCC study with data from different sites combined using a metaanalytical approach (see Section 17.14 Data Analysis). Sample size calculations were performed with the number of equally sized sites being 10, the overall anticipated CVE being 80% or 90%, the control to case ratio being 3:1, 1:1 or 1:3, the overall vaccination coverage among controls being 60%, 80% or 90%, and the proportion of the vaccination coverage covered by the vaccine of interest being 10%, 25%, 50%, or 75%. For each combination of these parameters, the sample sizes for which the expected 95% CI range was ≤30% were obtained. The technical specifications of the sample size calculations are given in Appendix 6.

For various CVE, total vaccination coverages, and different proportions of the total vaccination coverage covered by the brand of interest, the number of COVID-19 cases required to meet the CI criterion are summarised in Table 4. Irrespective of the other considered parameter combinations, having at least 1,134 COVID-19 cases yields expected 95% CI ranges  $\leq$ 30%. The corresponding total number of SARI cases needed to be enrolled can be found in Table 5 and having at least 2,210 SARI cases yields expected 95% CI ranges  $\leq$ 30% for a control to case ratio of 1:1. As this sample size was obtained for the crude CVE instead of the adjusted CVE, it was decided to conservatively adjust the targeted sample size to 1.2 x 1,134 = 1,360 COVID-19 cases and 1.2 x 2,210 = 2,652 SARI cases.

Finally, in case the observed share of the different COVID-19 vaccine brands or the overall vaccination coverage rate observed in the study differs largely from the settings described, the sample size

**C** VIDRIVE

Version 4.0

calculations will be updated accordingly. The sample size might also be updated in case vaccine effectiveness estimates against specific COVID-19 genetic variants are required.

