# Table 4. The required number of COVID-19 cases to allow the estimation of the CVE with an expected CI length ≤30%.

			Proportion of t	he total vaccina the brand of	-	e covered by
	Overall		10%	25%	50%	75%
Anticipated crude CVE	vaccination	Control to case ratio	-	ired number of exposed + expo		
80%	60%	3:1	1099	470	248	185
80%	80%	3:1	674	326	191	172
80%	90%	3:1	592	370	288	308
90%	60%	3:1	879	355	191	130
90%	80%	3:1	448	308	123	94
90%	90%	3:1	308	191	148	129
80%	60%	1:1	1105	460	255	187
80%	80%	1:1	666	330	211	172
80%	90%	1:1	608	348	286	258
90%	60%	1:1	855	363	190	128
90%	80%	1:1	440	208	127	93
90%	90%	1:1	343	203	148	128
80%	60%	1:3	1134	464	264	180
80%	80%	1:3	660	319	206	174
80%	90%	1:3	594	368	288	267
90%	60%	1:3	871	358	189	132
90%	80%	1:3	452	204	125	180
90%	90%	1:3	328	193	152	130

Table 5. The number of SARI cases required to allow the estimation of the CVE with an expected CI length ≤30%.

Proportion of the total vaccination coverage covered

					d of interest	
	Overall		10%	25%	50%	75%
Anticipated crude CVE	vaccination coverage	Control to case ratio		equired numb exposed + ex		
80%	60%	3:1	4534	1857	1054	720
80%	80%	3:1	2641	1277	825	694
80%	90%	3:1	2378	1473	1150	1067
90%	60%	3:1	3484	1431	757	528
90%	80%	3:1	1806	816	500	719
90%	90%	3:1	1314	773	610	518
80%	60%	1:1	2210	921	510	374

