The SARS-CoV-2 positivity rates within the SARI patients varies over time with the observed positivity rates since the start of the COVID-19 pandemic ranging from 20% to 80% (FISABIO, personal communication), implying that the potential case to control ratio would vary from 1:4 to 4:1 depending on calendar time. Future SARS-CoV-2 positivity rates in SARI patients are difficult to predict as they depend on both the successfulness of the COVID-19 vaccination programmes and the circulation of other respiratory pathogens. In case-control studies, the ideal number of controls is typically 1 to 3 times the number of cases [27]. To allow optimising the case-control ratio conditional on calendar time (with the latter being an important confounder in CVE studies), we allow for the possibility to 1) sample other hospital controls or modify the case capture definition in case the positivity rate would be high, and – when feasible and resource saving— to 2) restrict the number of controls per case in case the positivity rate would be low.

Confounding is a substantial concern for real-world studies on the effectiveness of COVID-19 vaccines.

As a result of the huge demand for COVID-19 vaccines and initially limited vaccine supplies, most European countries prioritised the vaccination of elderly people, residents and personnel in long-term

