#### Data generation workflow

#### Notation

Before describing the data generation workflow, the following parameters which act as input for the model have to be defined:

- 1.  $CVE_{x,overall}$ : the overall CVE of exposure x, the corresponding odds ratio is  $OR_{x,overall} = 1 \frac{CVE_{x,overall}}{100}$ .
- 2. c = P(unexposed | control): proportion of unexposed subjects among the controls
- 3.  $P_x = P(exposure \ x | exposed, control)$ : brand share of exposure x among the exposed
- 4. *r*: ratio of cases to control (that is, number of cases per one control)

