#### Summary measures of the simulation study

For each combination of the study characteristics, the measure of interest is obtained from the 500 simulations, e.g.

- The expected range of the 95% CI is defined as the mean range of the CI obtained from the 500 simulations.
- The expected lower half width of the 95% CI is defined as the mean lower half width of the CI obtained from the 500 simulations.
- The expected power to detect a CVE significantly different from 0 is defined as the proportion of the CI's that do not include 0.

For each measure, 95% Monte Carlo CIs were constructed based on the respective Monte Carlo standard errors observed in the simulations.

<sup>2 Hedeker, D., du Toit, S.H.C., Demirtas, H., et al. *A note on marginalization of regression parameters from mixed models of binary outcomes*. Biometrics, 2018. **74**(1): p. 354-361. DOI: 10.1111/biom.12707

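### Table 4's case numbers hardly respond to the control:case ratio, so the 1,134-case target is not supported at 1:3 for a 10% brand share; Tables 4 and 5 also disagree on which ratio is which

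*Protocol*

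**What the plan says.** Protocol section 15.11.1.1 sizes the primary-series objective by simulation over a grid of CVE (80% or 90%), control to case ratio (3:1, 1:1, 1:3), coverage among controls (60%, 80%, 90%) and brand share (10% to 75%), with "the number of equally sized sites being 10". For each combination, "the sample sizes for which the expected 95% CI range was ≤30% were obtained". Annex 6 adds that the expected range "is defined as the mean range of the CI obtained from the 500 simulations".

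The section concludes: "Irrespective of the other considered parameter combinations, having at least 1,134 COVID-19 cases yields expected 95% CI ranges" within the 30-point limit. The figure is Table 4's cell for CVE 80%, coverage 60%, share 10%, ratio 1:3. It is multiplied by 1.2, because the simulation is of the crude CVE, to give 1,360 cases. The matching SARI figure, 2,210 (2,652 after inflation), is tied to 1:1.

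Table 5 is titled "The number of SARI cases required to allow the estimation of the CVE with an expected CI length ≤30"% and should convert Table 4's cases into total enrolment. Tables 4 and 5 label the ratio as control to case. Annex 6 defines r the other way round, as the "ratio of cases to control (that is, number of cases per one control".

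On the ratio to be met in practice, section 17 reports past positivity of 20% to 80%, "implying that the potential case to control ratio would vary from 1:4 to 4:1 depending on calendar time".

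**The concern.** At a fixed number of cases, moving from 3:1 to 1:3 cuts the controls nine-fold. The log odds ratio must then become less precise, and the cases needed for a given interval length must rise. Table 4 shows no such rise, so its 3:1 and 1:3 blocks look like the 1:1 answer repeated with Monte Carlo noise.

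Two things depend on it. The case target is presented as safe at every ratio on the grid. And this is a master protocol: brand-specific protocols and the recalculation promised in section 15.11.1 would start from the same tables and the same ratio parameter.

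**Working it through.** **1. How flat Table 4 is.** In the worst cell the counts are 1,099 (3:1), 1,105 (1:1) and 1,134 (1:3). Over the 24 pairs, the 1:3 count divided by the 3:1 count has median 1.01, and 21 pairs lie within 8% of 1. The exceptions are 0.66 (204/308), 0.87 (267/308) and 1.91 (180/94).

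**2. What Annex 6's model implies.** Worst cell, assuming all brands share CVE 80% (OR 0.2); unexposed controls c = 0.40, brand-exposed controls 0.60 × 0.10 = 0.06.

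- P(unexposed | case) = 1/(1 + 0.2 × 0.60/0.40) = 0.769
- P(brand | case) = 0.2 × 0.06/0.40 × 0.769 = 0.0231
- With n cases and k controls per case, n × Var(log OR) = 1/0.0231 + 1/0.769 + (1/0.06 + 1/0.40)/k = 44.6 + 19.17/k

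This is 51.0 at 3:1, 63.8 at 1:1 and 102.1 at 1:3. At Table 4's own counts the variance is 51.0/1,099 = 0.046, 63.8/1,105 = 0.058 and 102.1/1,134 = 0.090, so the three entries cannot have equal precision.

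A closed-form length adds the between-site variance 0.05 over 10 sites and uses t with 9 df (2.262). At 1,134 cases and 1:3, SE = √(0.0901 + 0.005) = 0.308, and the length is 20 × (e^0.698 − e^−0.698) = 30.2 points. The same formula gives 23.6 at 1:1 and 21.1 at 3:1.

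**3. Simulation following Annex 6** (10 equal sites, variance 0.05, multinomial exposure). REML with modified Hartung-Knapp (HK), the analysis planned in section 15.14.4.2.1, with 0.5 added in sites that have a zero cell, reproduces the plan at 1:1. All 12 CVE 80% cells give 29.0-30.9 points at their printed sizes, and 1,105 cases give 29.0. At their printed sizes, the CVE 80% rows give about 18-26 points at 3:1 and 34-54 at 1:3.

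Expected length (points) for 1,134 cases in the worst cell:

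| Method | 3:1 | 1:1 | 1:3 |
|---|---|---|---|
| REML, modified HK, 0.5 rule | 25.0 | 28.4 | 34.3 |
| REML, modified HK, raw logistic fits | 26.1 | 29.8 | 35.1 |
| REML, unmodified HK, 0.5 rule | 21.6 | 24.9 | 29.1 |
| REML, unmodified HK, raw logistic fits | 20.4 | 23.8 | 23.4 |
| Sidik-Jonkman, HK | 21.1 | 24.8 | 30.9 |
| Sidik-Jonkman, modified HK | 28.5 | 33.2 | 43.0 |
| Wald | 21.3 | 23.9 | 28.7 |
| GEE, sandwich | 16.8 | 19.1 | 26.1 |

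Every variant gives a longer interval at 1:3 than at 3:1. With 1,360 cases at 1:3, REML with modified HK gives 31.2-31.5 points before any covariate adjustment.

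**4. Cases needed for 30 points in the worst cell.**

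| Method | 3:1 | 1:1 | 1:3 |
|---|---|---|---|
| REML, modified HK (range over zero-cell rules and runs) | 840-990 | 1,040-1,200 | 1,450-1,530 |
| REML, unmodified HK, 0.5 rule | 550 | 775 | 1,025 |
| Sidik-Jonkman, HK | 525 | 750 | 1,175 |
| Closed form | 575 | 718 | 1,150 |

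**5. Table 5 against Table 4.**

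- 1:1 block = 2 × Table 4's 1:1 block in 24 of 24 cells (largest difference 1); for example 2 × 1,105 = 2,210.
- 3:1 block = 4 × Table 4's **1:3** block in 24 of 24 cells (largest difference 2); 4 × 1,134 = 4,536 against 4,534.
- 1:3 block = 4/3 × Table 4's **3:1** block in 24 of 24 cells (largest difference 0.7); 4/3 × 1,099 = 1,465.3 against 1,465.
- Same-label products agree within 4 in only 2 of 24 cells at 3:1 and 9 of 24 at 1:3. The first cells would be 4 × 1,099 = 4,396 and 4/3 × 1,134 = 1,512.
- Table 5's 1:3 rows are labelled 50/70/90% coverage; the text and Table 4 use 60/80/90%.

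**The case against.** **The miss depends on the method.** Annex 6 names the Hartung-Knapp-Sidik-Jonkman estimator, not REML with modified HK. With unmodified HK or Sidik-Jonkman HK, 1,134 cases at 1:3 are borderline (29-31 points), and Wald and GEE meet 30. Section 15.14.4.2 also keeps GEE for sparse cells. This stands as a limit on how firmly the target can be said to fail. It does not rescue Table 4: the variants that make 1:3 acceptable do not reproduce the 1:1 rows, and they too need more cases at 1:3 than at 3:1 wherever the requirement was solved.

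**The miss is narrow.** At 1,134 cases and 1:3, under modified HK with the 0.5 rule, only 2 of the 12 CVE 80% cells exceed 30, both at 10% share: about 34-35 at 60% coverage and about 31.6 at 90%. The other ten give 15-29. The 34-54 range belongs to the smaller printed cell sizes, and a reader should not infer from it that the target fails across the grid.

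**The plan can respond.** Section 15.11.1 promises recalculation if the settings differ widely, section 15.12 plans measures for high positivity, and the abstract states its SARI figure at 1:1. These limit the consequence but do not correct the sentence.

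**Section 17 does not forecast the study's ratio.** A reader might infer that the study is expected to run at four cases per control. The text gives a potential range by calendar time from past positivity and calls future rates hard to predict. It shows only that ratios beyond 1:3 have been seen.

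**Conclusion.** Table 4's 3:1 and 1:3 blocks cannot be right as printed under Annex 6's model, and the claim that 1,134 cases suffice whatever the other parameters is not supported at 1:3 for a 10% brand share. Under the planned analysis the shortfall is about 4-5 points at 1,134 cases and about 1.5 at 1,360. That uses up the 1.2 factor before the adjustment it was meant for. At 3:1 the printed figure is too high.

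This rests on equal CVE across brands, crude estimates, and REML with modified HK, chosen because it is the planned analysis and reproduces the CVE 80% rows at 1:1. The CVE 90% rows at 1:1 were not reproduced: about 22-25 points with the 0.5 rule, and 32-33 with raw fits in the two cells checked. They carry no weight here. Table 7 in section 15.11.1.3 does rise with fewer controls (1,672 at 1:1, 2,498 at 1:3), but its 3:1 rows repeat the 10% value under 75%, so it is supporting evidence only.

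The row exchange between Tables 4 and 5 is exact. A reader might conclude that Table 5 is the faulty one. The document does not show that: since Annex 6's r is cases per control, Table 4's labels may be the reversed ones. In that case 1,099 is the 1:3 figure, and it also misses (34.6 points). The exchange alone moves the first-row totals by only about 3%; the missing ratio effect is the larger error. Nor is the headline SARI target undermined: 2,210 and 2,652 are stated for 1:1 and are consistent there.

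**What to change.** - Check how the ratio was passed to the simulation, given the opposite definitions in Annex 6 and the tables, and use one definition throughout.
- Re-run the 3:1 and 1:3 blocks of Table 4 with the ratio applied.
- Correct the ratio and coverage labels so that each Table 5 row follows from the same-labelled Table 4 row.
- Limit 1,134 and 1,360 to 1:1, drop the claim that they hold irrespective of the other parameters, and state a target for each ratio.
- Name the pooling method and zero-cell handling behind the tables, since the requirement depends on both.

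The cost is 48 simulation cells and a restated paragraph. The 1:3 requirement becomes less favourable: about 1,450-1,530 crude cases in the worst cell, or 1,740-1,836 after the 1.2 factor, against 1,360. The 3:1 requirement becomes more favourable: 840-990 crude cases, or 3,360-3,960 SARI patients, against 4,534.

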# Table 4. The required number of COVID-19 cases to allow the estimation of the CVE with an expected CI length ≤30%.

			Proportion of t	he total vaccina the brand of	-	e covered by
	Overall		10%	25%	50%	75%
Anticipated crude CVE	vaccination	Control to case ratio	-	ired number of exposed + expo		
80%	60%	3:1	1099	470	248	185
80%	80%	3:1	674	326	191	172
80%	90%	3:1	592	370	288	308
90%	60%	3:1	879	355	191	130
90%	80%	3:1	448	308	123	94
90%	90%	3:1	308	191	148	129
80%	60%	1:1	1105	460	255	187
80%	80%	1:1	666	330	211	172
80%	90%	1:1	608	348	286	258
90%	60%	1:1	855	363	190	128
90%	80%	1:1	440	208	127	93
90%	90%	1:1	343	203	148	128
80%	60%	1:3	1134	464	264	180
80%	80%	1:3	660	319	206	174
80%	90%	1:3	594	368	288	267
90%	60%	1:3	871	358	189	132
90%	80%	1:3	452	204	125	180
90%	90%	1:3	328	193	152	130

Table 5. The number of SARI cases required to allow the estimation of the CVE with an expected CI length ≤30%.

Proportion of the total vaccination coverage covered

					d of interest	
	Overall		10%	25%	50%	75%
Anticipated crude CVE	vaccination coverage	Control to case ratio		equired numb exposed + ex		
80%	60%	3:1	4534	1857	1054	720
80%	80%	3:1	2641	1277	825	694
80%	90%	3:1	2378	1473	1150	1067
90%	60%	3:1	3484	1431	757	528
90%	80%	3:1	1806	816	500	719
90%	90%	3:1	1314	773	610	518
80%	60%	1:1	2210	921	510	374

**C VIDRIVE** 

COVIDRIVE Master Protocol for hospital-based TNCC studies

80%	80%	1:1	1332	659	422	345
80%	90%	1:1	1217	697	572	517
90%	60%	1:1	1710	726	380	255
90%	80%	1:1	880	415	254	186
90%	90%	1:1	686	406	295	255
80%	50%	1:3	1465	626	330	247
80%	70%	1:3	899	435	255	230
80%	90%	1:3	789	493	384	410
90%	50%	1:3	1172	473	255	174
90%	70%	1:3	598	410	164	126
90%	90%	1:3	410	255	197	172

# 15.11.1.2 Primary vaccination, variants of interest

The sample size calculations for calculation of the brand-specific CVE against SARS-CoV-2 variants of interest were done in the same manner as for the sample size calculations for the primary analysis with the exception that the required sample size had to lead to an expected range of the 95% CI  $\leq$ 70%. The required number of COVID-19 cases with the variant of interest ranged from 68 to 500. For the brand-specific analyses, the required number of COVID-19 cases with the variant of interest will be selected based on the observed vaccination coverage and brand proportions.

					of interest	ge
	Overall		10%	25%	50%	75%
Anticipated vaccination		Control to	Required numb	er of COVID-1	9 cases with the	e variant of interest
crude CVE	coverage	case ratio		unexposed +	exposed any br	and)
80%	60%	1:1	472	203	108	84
80%	80%	1:1	276	146	92	73
80%	90%	1:1	258	164	128	120
90%	60%	1:1	506	209	114	80
90%	80%	1:1	244	128	82	68
90%	90%	1:1	208	128	93	84

Proportion of the total vaccination coverage covered by the

# 15.11.1.4 Interim analysis

An interim analysis is planned when data on a sufficient number of COVID-19 cases, vaccinated with the brand-specific vaccine as primary series or an additional last dose, has been collected to provide an expected 95% CI range  $\leq$ 15% or a power of 50% with the same assumptions as described in the previous sections.

#### 15.11.2 Time to number of cases

The institute for Health Metrics and Evaluation (IHME) has developed a deterministic SEIR (susceptible – exposed – infectious – recovered) compartmental framework to predict SARS-CoV-2 infections, hospitalisations and deaths for over 380 locations worldwide (http://www.healthdata.org/covid)[11].

For study planning, the continuously updated IHME projected COVID-19 hospitalisation rates will be used to predict the number of COVID-19 cases that is expected to be reached by a certain point in time, taking into account the catchment area of the study sites participating to the study. The number

of vaccinated COVID-19 cases by brand are predicted by additionally accounting for the anticipated CVE and brand-specific vaccination coverage.

#### 15.11.3 Case-control ratio

Including more than three controls per case does not lead to a notable increase in the precision of the estimates. When possible and resource-saving, the number of controls sampled per case by calendar week will be restricted. Restricting the number of controls might be possible for some sites where SARI patients can be enrolled after their SARS-CoV-2 status is known and before they are transferred to either the COVID-19 or non-COVID-19 area within the hospital. This will be described as part of the patient flow, when applicable.

# 15.12 Unfavourable COVID-19 positivity rate among SARI cases

The COVID-19 positivity rate among SARI cases will be closely monitored over time. Positivity rates that are too high or too low result in an inefficient study requiring large sample sizes (SARI cases) to obtain limited precision of the vaccine effectiveness estimates. When the positivity rate is unfavourably high, changing the case capture definition (currently SARI) or enrolling other hospital controls (e.g. patients presenting to the emergency department for reasons other than SARI) will be considered, as a separate analysis. When the positivity rate is low, the weekly number of controls per case for the prospective recruitment will be restricted when possible to a maximum of three. For retrospective data, we will randomly select controls from the pool available for each study contributor and match to cases based on calendar week.

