# **15.2 Study contributors (sites)**

This is a multi-country, multi-centre study, with hospital sites in Europe. The participating studies sites are described in Table 1.

The participating study sites are either individual hospitals or hospital networks. Depending on the hospital, the data collection will be a prospective primary data collection and in some study sites, data will additionally be retrospectively retrieved from the existing hospital databases and linked data.

For every participating study site, a site-specific protocol will be written, describing details on patient flow, data collection, laboratory tests and genomic sequencing.

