#### 15.3.1 Inclusion criteria

Individuals (patients) need to fulfil the following inclusion criteria:

• Ever eligible for COVID-19 vaccination following the national/regional immunisation recommendations prior to hospital admission

AND

• Willing and able to provide informed consent, when applicable, obtained from the patient or from the patient's Legally Acceptable Representative(s) (LAR)

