# **15.7 SARI patient identification**

Depending on the study site, the SARI patient identification will be different. Hospitalised SARI patients will be identified prospectively (e.g. during consultation in the ED or during a pneumology consultation) or retrospectively by hospital database search or from respiratory samples sent to the virology laboratory.

«For every participating study site, the patient flow will be documented in detail.»

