# 15.14.4 Statistical analyses

# 15.14.4.1 Site-specific CVE

For every study site, the crude and confounder-adjusted brand-specific CVE against laboratoryconfirmed COVID-19 disease will be estimated as:

VE = (1 – OR) x 100%,

CINICRIVE

where *OR* denotes the crude or confounder-adjusted odds ratio, comparing the odds of vaccination among COVID-19-positive study participants to the odds of vaccination among COVID-19-negative study participants.

Confounder-adjusted CVE estimates will be derived from multivariable logistic regression models. The analysis to estimate brand-specific CVE will account for the differences in approved indications, discarding from the analysis patients for which the vaccine brand of interest is not indicated. All CVE estimates will be adjusted for calendar time.

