### **ANNEX 4: STUDY-SPECIFIC COMMON MINIMUM DATASET**

Nr	Variable name		Description	Additional info	Variable format	Values/coding	Mandatory
SITE II	DENTIFICATION						
	idsite		Site identifier		Text	As described in the Study Plan	x
	country		Country identifier		Text	As described in the Study Plan	х
PATIE	NT IDENTIFICATION	I					
	idpatient		Patient identifier	Identifier also contains country and site identifier	Text	As described in the Study Plan	x
	sex		Sex		Numeric (categorical)	1=Male 2=Female X=Sex-neutral	x
	ageyears		Age in years at admission		Numeric		Х
ADMI	SSION DATA						
	onsetdate		Date of first symptom onset		DD/MM/YYYY	Date within the study period	Х
	admissiondate		Date of hospitalisation	First point of contact (arrival at Emergency Department)	DD/MM/YYYY	Date within the study period	x
	SARI		SARI patient		Numeric (categorical)	0=No	х

CIDRIVE

						COVIDRIVE
					1=Yes	
					9999=No information	
					0=No	
	fever	History of fever or measured fever >=		Numeric (categorical)	1=Yes	x
		38°C		,	9999=No information	
					0=No	
	cough	Cough		Numeric (categorical)	1=Yes	x
			, , ,	9999=No information		
					0=No	
	shortbreath	Shortness of breath		Numeric (categorical)	1=Yes	x
	Shortbreath		itumene (euregeneur)	9999=No information	~	
					0=No	
	anos_dysg	Sudden onset of anosmia, ageusia or		Numeric (categorical)	1=Yes	x
	dysgeusia	dysgeusia	Numeric (categorical)	9999=No information	~	
	JSION/EXCLUSION CR	ITERIA				
INCLU					0=No	
	vacc_eligible	zible Eligible for COVID-19 vaccination at Numeric (categorical	Numeric (categorical)	• • • • •		
		time of hospitalisation			1=Yes	
		Communication with patient/Legally			0=No	
	comm	Authorised Representative		Numeric (categorical)	1=Yes	Х
		Autionseu Representative			8888=Not applicable	
					0=No	
	consent	Consent/assent given		Numeric (categorical)	1=Yes	Х
					8888=Not applicable	
					0=Patient	
		If consent is given, who gives the			1=Legally Authorised	
	Consentwho1	consent?		Numeric (categorical)	Representative	Х
					8888=Not applicable	
			In case		- F.F	
			consent/assent			
	Consentwho2		needs to be given by		0=Patient	
		If consent is given, who gives the	both	Numeric (categorical)	1= Legally Authorised	x
	CONSCIEWINGZ	consent?	Parent/tutor/guardi	Rumene (categorical)	Representative	
			an and young		8888=Not applicable	
			patient			
			patient			1

						COVIDRIVE
	consentdate	Date of consent given		DD/MM/YYYY	Date within the study period 8888 = Not applicable	х

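### Annex 4 has no field for prospective versus retrospective collection, so at sites with both streams possible confounding of the site CVE by stream can be neither reliably tested nor adjusted for

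*Protocol*

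**What the plan says.** Section 15.2 describes prospective primary data collection and adds that "in some study sites, data will additionally be retrospectively retrieved from the existing hospital databases and linked data". Section 15.7 separates the two routes of identification: prospectively during consultations, "or retrospectively by hospital database search or from respiratory samples sent to the virology laboratory".

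Section 15.12 gives each stream its own control-sampling rule for periods of low positivity. For one, "the weekly number of controls per case for the prospective recruitment will be restricted when possible to a maximum of three". For the other: "For retrospective data, we will randomly select controls from the pool available for each study contributor and match to cases based on calendar week". No control-to-case ratio is given for the retrospective stream. Section 15.11.3 adds that restriction might be possible at sites where "SARI patients can be enrolled after their SARS-CoV-2 status is known".

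Consent (section 15.3.1) is conditional and not tied to a stream: "Willing and able to provide informed consent, when applicable".

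The unit of estimation in section 15.14.4.1 is the site: "For every study site, the crude and confounder-adjusted brand-specific CVE" is to be estimated, and all estimates are adjusted for calendar time. The sensitivity analyses listed in section 15.14.4.5 include none by stream, although that section leaves room for others in the SAP.

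Under sections 15.13.1 and 15.13.2, sites convert their patient-level data to the Annex 4 dataset and upload that. Annex 4 opens with "Site identifier", followed by country and patient identifiers. It also codes the source of the vaccination information (registry, medical record or card). No variable records whether the patient was collected prospectively or retrospectively.

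**The concern.** At a mixed site, two groups of patients enter one logistic model. They were found by different routes, and their controls were sampled under different rules. For stream to confound the vaccine odds ratio, it must be related to vaccination among controls and to case status among the unvaccinated. The sampling rules can produce the second relation. The first is plausible, because the routes of identification differ and consent may filter the streams differently.

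If both hold, calendar-time adjustment does not help where the streams share the same weeks. Pooling across sites does not help either, because the mixing is inside the site. The usual answer is a stratum term, but that needs a variable that the specified dataset does not contain. This is why the point belongs to the protocol: the SAP can choose any model, but it cannot stratify on a field that was not collected.

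**Working it through.** **Is there a stream field?** Annex 4 was read field by field. The nearest item is the consent variable, with its not-applicable code. Consent depends on national or regional ethics rules (section 18.3), so a not-applicable code does not identify a retrospective patient.

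**How large could the effect be?** The protocol gives no figure to reproduce. An expected-count illustration uses these inputs:
- True CVE 80% (OR 0.20) in both streams, one of the anticipated values in section 15.11.1.1.
- Control-to-case ratios of 3:1 and 1:1, both used in section 15.11.1.1. Assigning them to streams is an assumption.
- Coverage among controls of 85% prospective and 75% retrospective, and 500 cases per stream in the same weeks. All of these are assumptions.

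With control coverage c, the odds of vaccination among cases are 0.20 × c/(1 − c).

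- Prospective cases: 0.20 × 0.85/0.15 = 1.133, so 265.6 vaccinated and 234.4 unvaccinated.
- Retrospective cases: 0.20 × 0.75/0.25 = 0.600, so 187.5 vaccinated and 312.5 unvaccinated.
- Cases together: 453.1/546.9 = 0.8286.

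Collapsing over stream gives:

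1. *3:1 prospective, 1:1 retrospective.* Vaccinated controls 1,275 + 375 = 1,650; unvaccinated 225 + 125 = 350; odds 4.714. OR = 0.8286/4.714 = 0.176, **CVE 82.4%**.
2. *Same ratios, coverages reversed.* Controls 1,125 + 425 = 1,550 and 375 + 75 = 450; odds 3.444. OR = 0.241, **CVE 75.9%**.
3. *Equal ratios (1:1 in both).* Controls 425 + 375 = 800 and 75 + 125 = 200; odds 4. OR = 0.207, **CVE 79.3%**. With 3:1 in both, 2,400/600 gives the same result.
4. *Equal coverage (80% in both).* Case odds 0.20 × 4 = 0.8, control odds 4, OR = 0.20, **CVE 80.0%** whatever the ratios.

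Varying the prospective share of cases (25%, 50%, 75%) gives these collapsed CVEs:

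| Coverage, prosp./retro. | Controls per case, prosp./retro. | 25% | 50% | 75% |
|---|---|---|---|---|
| 85/75 | 3 / 1 | 82.3 | 82.4 | 81.5 |
| 85/75 | 1 / 3 | 77.7 | 75.9 | 75.8 |
| 85/75 | equal | 79.5 | 79.3 | 79.4 |
| 90/70 | 3 / 1 | 83.4 | 83.7 | 82.5 |
| 90/70 | 1 / 3 | 74.1 | 69.2 | 68.0 |
| 90/70 | equal | 77.8 | 76.9 | 77.4 |

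Equal ratios therefore do not remove the bias when the coverage gap is large. In case 3, the unvaccinated case-to-control ratios still differ by stream: 234.4/75 = 3.1 against 312.5/125 = 2.5.

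Stratifying by stream returns 80.0% in every row, because the within-stream OR is 0.20 by construction.

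**The case against.** A reader might infer that the site CVE *is* confounded by stream. The documents do not support that, for four reasons.

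- **Ratios.** Section 15.12 states no retrospective ratio. The abstract gives one general limit of three controls per case per week without distinguishing streams, and random week-matched selection may simply be how that limit is applied to database patients. The prospective cap itself holds only at low positivity and when possible. Different sampling fractions alone do not bias an odds ratio.
- **Selection.** It is tempting to contrast consenting prospective patients with unselected retrospective ones. Consent is required only where applicable, a representative may give it, and section 18.3 allows special procedures for patients in poor health. Nothing ties waived consent to the retrospective stream, and no coverage gap by stream is documented.
- **Timing and adjustment.** The protocol does not say that the streams share weeks. If they do not, calendar-time adjustment can remove the effect. The illustration is also crude: only differences left after covariate adjustment matter.
- **Feasibility.** Whoever samples the retrospective controls must know which records are retrospective. Annex 4 is a minimum dataset, and its site codes are deferred to the Study Plan, so a site-by-stream code could be introduced there.

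A shift of about 2 points is also small beside the 30-point interval length that the sample size targets.

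The first three reasons stand and limit the claim to possible confounding at some sites. The last shows that the gap is easy to close, not that it is closed: no text requires the stream to be recorded in the uploaded data. A bias of this kind also does not shrink as patients accrue.

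**Conclusion.** The point holds as a limited one. At mixed sites the protocol sets separate control-sampling rules by stream when positivity is low, fits one model per site, and specifies an upload dataset that does not identify the stream. Whether stream confounds the site CVE is unknown. It would do so only if vaccination odds differ by stream after adjustment and the streams overlap in calendar time.

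Under the assumed 85%/75% coverage, an 80% CVE would read as about 82%, 76% or 79%, depending on the ratios and on which stream has the higher coverage. Under 90%/70% the range is 68.0% to 83.7%. Under equal coverage there is no error. These are illustrations, not estimates of the actual bias. The established defect is that the specified data do not allow the question to be reliably checked or corrected. It is worth fixing because the remedy is cheap.

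**What to change.** 1. **Annex 4:** add a mandatory field for data-collection stream (1 = prospective, 2 = retrospective).
2. **Section 15.12:** state the control-to-case ratio for retrospective sampling.
3. **Section 15.14.4.1:** at sites with both streams, include stream as a stratum term in the site model, or make site-by-stream the unit that is pooled.
4. **Section 15.14.4.5:** list CVE by stream as a sensitivity analysis.

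The cost is one field whose value each site already knows, including for records already collected, and one model term. The downside is a slight loss of precision at sites where the second stream is small.
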